- as downloaded data files saved on secure, password-protected institutional computers (e.g. CGM data, dietary recall data, etc)
 - Diet recall via ASA24 and DietID will be directly entered into each website. ASA24 is a free, web-based dietary assessment tool that is run by the National Institutes of Health. ASA24 data is associated with study ID and does not capture any personally identifiable information from participants. DietID is a web-based dietary assessment tool used for clinical and research purposes. DietID is associated with unique access and does not require identifiable information from participants. Completed ASA24 and DietID surveys will be stored on web-based servers and periodically downloaded throughout the study.
- in REDCap, a 21 CFR Part 11-compliant data capture system. REDCap includes password protection and internal quality checks, including field validation to help identify inconsistent, incomplete, or inaccurate data. Data entered into REDCap will come directly from the original source data; or in some cases, REDCap may serve as the source data (e.g. protocol deviations; participant response to surveys via REDCap; participant supply management, etc.). REDCap maintains a built-in audit trail that logs all user activity and all pages viewed by every user, this includes entering data, exporting data, modifying a field, running a report, or adding/modifying a user, etc.

Data collection is the responsibility of the delegated study staff under the supervision of the Investigator. The Investigator is responsible for ensuring the accuracy, completeness, legibility, and timeliness of the data reported.

25. Data Monitoring

Investigators and delegated study staff will monitor study data for completeness and quality. Several strategies will be used to cross-check data accuracy and integrity, including staff checklists for each participant contact.

26. Data Sharing

As allowable by the governing IRB and organizational legal requirements, select, de-identified datasets for the completed project will be made available. All datasets will be shared in compliance with human subject protection and Health Insurance Portability and Accountability Act (HIPAA) privacy regulations.

This trial will be registered at ClinicalTrials.gov; trial results will be added to ClinicalTrials.gov after study completion.

27. Record Keeping and Retention

Clinical research records, including IRB records, and other records related to the study will be stored in a manner that ensures privacy, confidentiality, security, and accessibility while the clinical research is being conducted and after the study is completed.

The site will retain all study records, including HIPAA-related documents, after the study completion per institutional policy. Physical documents will be consolidated and stored in boxes in a secure location after study completion and electronic documents will be maintained in designated research study folders on the institutional drive in accordance with the institutional data retention guidelines. After the record retention period has been met, study-related materials may be destroyed.

28. Confidentiality and Privacy

Participants will be assigned a unique ID number after consent. Whenever possible, participant records and datasets will contain the unique ID only. The participant will be informed during the study screening process and via the ICF that their personal study-related data will be accessible by study staff and individuals within the International Diabetes Center throughout the duration of and after the study. Participants will be informed that by using CGM, their information will also be available to the CGM device manufacturer, Dexcom. Participants will need a personal account for use with the Dexcom systems. Participants will need to provide personal information (e.g. name, date of birth, email, etc) for the Dexcom accounts. Data in the Dexcom apps and associated websites is secure to the extent provided by the manufacturer. Participant data and any related records may also be made accessible to regulatory authorities or as required by law.

The confidentiality of all participant information and data are protected to the extent allowed by law. Records will be kept confidential in accordance with HIPAA privacy regulations. Investigators and personnel will not use data or records for any purpose other than conducting the study; however, de-identified participant data may be used for educational purposes and shared in medical journals, at scientific meetings, or in similar settings. No identifiable data will be used for future study without first obtaining IRB approval.

29. Ethics and Protection of Human Subjects

This protocol and any amendments, ICFs, recruitment materials, and all participant-facing materials will be submitted to the IRB for review and approval. Approval of the protocol and consent forms will be obtained before any participant is enrolled. Approval of protocol amendments and changes to the consent forms will be obtained before any changes are implemented. The decision of the IRB concerning the conduct of the study will be made in writing to the Investigator. A copy of the initial IRB approval letter will be provided to the study funder (American Diabetes Association) before commencement of this study.

This study will be conducted in full accordance with all applicable Federal and state laws and regulations including 45 CFR, and the HIPAA Privacy Rule. Any episodes of non-compliance will be documented. The Investigators will perform the study in accordance with this protocol, will obtain consent, and will report unexpected problems in accordance with IRB policies and procedures. Collection, recording, and

CGM Initiation in People with T2D

reporting of data will be accurate and will ensure the privacy, health, and welfare of research participants during and after the study.

30. Conflict of Interest

Study leadership in conjunction with the HealthPartners Institute has policies and procedures for all study group members to disclose conflicts of interest and to establish a mechanism for the management of all reported dualities of interest. Persons who have a perceived conflict of interest will be required to have such conflicts managed in a way that is appropriate to their participation in the design and conduct of this trial.

31. References

1. CDC.gov. Diabetes Fast Facts. <https://www.cdc.gov/diabetes/basics/quick-facts.html>. Updated September 30, 2022. Accessed January 23, 2023.

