1. Difference in total HEI score between groups during the post-intervention period	Automated Self-Administered 24-hour (ASA24 [®]) survey-derived total HEI-2015* score; score based on two diet recalls per assessment period, collected via web-based survey (ASA24 Version 2022 or later)

CGM Initiation in People with T2D

*Survey-derived HEI-2015 scores may be replaced with a newer scoring option if both scoring and analysis code become available

Exploratory Outcomes

Outcome	Assessment Method

1. Change in other CGM-derived core metrics from baseline to post-intervention; including as described by the 24-hour period, daytime period (6AM to 11:59PM), and nighttime period (12AM to 5:59PM):
 
 • number of days CGM device is worn • % time CGM sensor is active • mean sensor glucose mg/dL • % coefficient of variation • glucose management indicator (GMI) • % time above >250 mg/dL • % time above >180 mg/dL • % time below <70 mg/dL • % time below <54 mg/dL 	
See CGM-related outcome measures described above

2. Other CGM-derived metrics:
 
 • Change in % time in tight range (% time with glucose 70-140 mg/dL) from baseline to post-intervention • % of participants reaching CGM-derived consensus targets during post-intervention²⁶ 
 ○ % reaching >70% TIR (% time with glucose 70-180 mg/dL) ○ % reaching ≥5% improvement in TIR (% time with glucose 70-180 mg/dL) compared to baseline ○ % reaching >70% time TIR (% time with glucose 70-180 mg/dL) and reaching a ≥5% improvement in time in range compared to baseline 	
See CGM-related outcome measures described above

3. Describe HEI component scores by group during the post-intervention period
	
ASA24 survey-derived HEI-2015* component scores; scores based on two diet recalls per assessment period, collected via web-based survey (ASA24 Version 2022 or later)

4. Change in additional nutrition metrics from baseline to post-intervention
 
 • total energy intake • macronutrients and fiber 	
ASA24 survey-derived values based on two diet recalls per assessment period, collected via web-based survey (Version 2022 or later)

CGM Initiation in People with T2D

 select micronutrients 	

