5. Change in patient-reported outcome survey scores from baseline to post-intervention 
 Diabetes Distress Scale-17 Score Diet Adherence Efficacy Survey Score 	Validated Diabetes Distress Scale Score, ⁴⁰ Diet adherence survey score, Efficacy survey scores; surveys administered via REDCap
6. Change in HbA1c from baseline to post-intervention	HbA1c assessed by either point-of-care fingerstick or venous draw
7. Change in body mass index (BMI) and body weight from baseline to post-intervention	Calibrated clinic scale and stadiometer; BMI calculated from measured weight and height
8. Describe fidelity to the intended intervention, including dose and content delivered, content enacted, and satisfaction	Data collection from study staff via paper documentation; and participant surveys administered via REDCap
9. Describe post-intervention patient-reported behavioral mechanisms	Participant surveys administered via REDCap

12. Phase 2 Study Outcome Measures

The Phase 2 follow-up assessment period is approximately 4 months and begins the day after Phase 1 is complete (approximately Day 51 to Day 180).

CGM-related outcome measures include approximately 10 days of CGM data collection during the baseline, post-intervention, and follow-up assessment periods. CGM data collection for the baseline and post-intervention are described under Phase 1 Study Outcomes Measures. CGM data at follow-up will be collected in the same way as baseline, which is up to 10 days of CGM data from a Dexcom G7 sensor paired with a physically blinded Dexcom receiver.

Primary Outcome

Outcome	Assessment Method
1. Change in CGM-derived TIR (% time with glucose 70-180 mg/dL) from post-intervention to follow-up for combined NFA and SDA arms	See CGM-related outcome measures described above

Exploratory Outcomes

Outcome	Assessment Method
1. Change in other CGM-derived core metrics from post-intervention to follow-up: 
 number of days CGM device is worn % time CGM sensor is active 	See CGM-related outcome measures described above

CGM Initiation in People with T2D

 • mean sensor glucose mg/dL • % coefficient of variation • glucose management indicator (GMI) • % time above >250 mg/dL • % time above >180 mg/dL • % time below <70 mg/dL • % time below <54 mg/dL 	

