General Approach for Statistical Analyses in Phase 2

The general approach for the analysis of Phase 2 will follow the approach used for Phase 1, but with modifications to the contrasts computed. The analytic models will utilize general and generalized linear mixed model repeated measures analysis and include fixed effects for study arm, time, their interaction, variables used in stratification, and a random intercept for patient. Each model will report the model-derived estimate (and 95% confidence interval) for the endpoint by study arm and by time period. The link function and error distribution selected for each model will be based on the distribution of the endpoint. Analysis will be conducted with both the modified ITT sample for Phase 2 and the PP sample.

The key analytic test for the primary endpoint will be based on planned contrasts (effect slices) reflecting the change from the end of the intervention period to the follow-up period, with study arm data pooled. Model-derived estimates of change across these two periods will be reported along with 95% confidence intervals. For the primary outcome, effect slices will also be tested for within-study arm change from the end of the intervention period to the follow-up period. A final Statistical Analysis Plan will specify further analytic detail and inclusion of any additional covariates.

CGM Initiation in People with T2D

Planned Interim Analysis

Not applicable

Sub-Group Analyses

There are no planned sub-group analyses or analyses to assess heterogeneity of treatment effects.

Analysis of Exploratory Endpoints in Phase 1

Exploratory endpoints are listed in the section Phase 1 Study Outcome Measures: Exploratory Outcomes.

Analysis of exploratory endpoints will follow the analytic framework used for the primary endpoint and will report model-derived estimates and statistical testing of the interaction contrast. However, the test of this interaction is considered hypothesis-generating and is not necessarily powered adequately. Some exploratory analyses will be post-only analyses using the same analytic framework but will include only fixed effects for study arm and stratification factors, but not an effect for time or their interaction. There will be no control for multiple testing in exploratory analyses. In sensitivity analysis, models will adjust for key prognostic factors selected a-priori.

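### Phase 1 exploratory outcome 1 ends the nighttime window at 5:59PM, so 12 of its 18 hours are also daytime hours; probably a slip for 5:59AM

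*Combined protocol and SAP*

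**What the plan says.** Section 11 (Phase 1 Study Outcome Measures), Exploratory Outcomes, item 1 is worded "Change in other CGM-derived core metrics from baseline to post-intervention; including as described by the 24-hour period" and then adds two sub-periods: "daytime period (6AM to 11:59PM), and nighttime period (12AM to 5:59PM"). Nine metrics are listed under it: days of wear, % time the sensor is active, mean glucose, % CV, GMI, and % time above 250, above 180, below 70 and below 54 mg/dL.

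Section 23 (Analysis of Exploratory Endpoints in Phase 1) puts these outcomes through the same modelling framework as the primary endpoint, with an estimate and a test of the arm-by-time interaction. It adds that "the test of this interaction is considered hypothesis-generating and is not necessarily powered adequately". The same section leaves further detail on exploratory analyses to a final SAP, which is not part of the document reviewed.

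The Phase 2 counterpart in section 12, "Change in other CGM-derived core metrics from post-intervention to follow-up", gives no day/night split, so it offers no second definition to compare.

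**The concern.** A day and a night period reported beside a 24-hour period should divide the 24 hours between them. These two do not. The stated night runs through the morning and afternoon to just before 6PM, and all of that time after 6AM already belongs to the stated day.

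At stake is the meaning of the night results. Each would come with an arm-by-time estimate and a test, and readers would take it to describe overnight glucose. An 18-hour window gives plausible values, so the output itself would not reveal the error. The trial's hypothesis works through food choices, so readers will naturally ask when in the day glucose changed.

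**Working it through.** **Inputs.** All clock times come from section 11, Exploratory Outcomes, item 1. The seven-day minimum and ten-day target for CGM data come from sections 11 and 23. There is no sample size, power or alpha figure to reproduce; the check is on clock time, with end minutes included.

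**Windows as written**

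| Period | Clock times | Hours |
|---|---|---|
| Day | 6AM to 11:59PM | 18 |
| Night | 12AM to 5:59PM | 18 |
| Sum | | 36 |
| Shared | 6AM to 5:59PM | 12 |

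Share of the stated night that is also day: 12/18 = 67%. Leaving out the end minutes gives 11.98/17.98 = 66.6%.

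**Night ending at 5:59AM.** Night is 6 h and day 18 h; 18 + 6 = 24 h, with no overlap and no gap. Given the stated day and a 12AM start, any later end time overlaps the day and any earlier one leaves a gap.

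**Data drawn on per participant**
- Seven days: 7 × 18 = 126 h as written, against 7 × 6 = 42 h.
- Ten days: 10 × 18 = 180 h, against 10 × 6 = 60 h.

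**Effect on the night estimate, if programmed as written.** This applies to the five metrics that are averages over time: mean glucose and the four % time metrics. Let d be an effect confined to one part of the day, with even sensor coverage.

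| Where the effect d lies | Night as written | Night ending 5:59AM |
|---|---|---|
| 12AM to 5:59AM | (6/18)d = 0.33d | d |
| 6AM to 5:59PM | (12/18)d = 0.67d | 0 |
| 6PM to 11:59PM | 0 | 0 |

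An effect equal at all hours would be estimated correctly under either window, so the distortion arises only when the effect varies over the day.

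**Uneven coverage.** The documents give no coverage by hour. As an assumption, let coverage in 12AM to 5:59AM be c times that in 6AM to 5:59PM, with c from 0.8 to 1.25.
- Overnight effect: 6c/(6c + 12) = 4.8/16.8 = 0.29 to 7.5/19.5 = 0.38 of d.
- Morning and afternoon effect: 12/(6c + 12) = 12/16.8 = 0.71 to 12/19.5 = 0.62 of d.

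The conclusion does not change over that range. No figure is given for % CV (not linear over hours), GMI (formula not stated), % time the sensor is active, or days of wear.

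**The case against.** The strongest reply is that this is an obvious typing error. The day starts at 6AM in the same phrase, nobody would choose a night that ends just before 6PM, and a programmer would be likely to notice two windows adding up to 36 hours. Detailed specification is also left to a later SAP, where the window may already be right. The outcome is exploratory, has no multiplicity control, and no day-versus-night contrast is planned. Finally, the PM might have come from file conversion.

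Most of this bears on weight, and it is why the point ranks low. It does not remove the error. The phrase is the only operative definition of the window in the document. If a programmer corrects it silently, the reported analysis departs from the protocol without a record. A SAP not yet seen cannot be assumed to correct it. A conversion error is unlikely, since the surrounding text is clean, but the master protocol file should be checked.

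**Conclusion.** The inconsistency is real: 12 of the 18 stated night hours (67%) are also stated daytime hours. It is probably an AM/PM slip.

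The harm depends on the window being programmed as written. In that case a purely overnight effect would be cut to about one third, and about two thirds of a morning-and-afternoon effect would appear as a night effect. These fractions assume even sensor coverage and hold only for the five time-averaged metrics.

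The consequence is confined to the night results of Phase 1 exploratory outcome 1. The primary TIR endpoint, the secondary HEI endpoint, the sample size, the 24-hour and daytime metrics, and all Phase 2 outcomes are unaffected. This is a minor correction, worth making before programming starts.

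**What to change.** In section 11, Exploratory Outcomes, item 1, change the end of the nighttime window from 5:59PM to 5:59AM, after checking the wording in the master protocol file. State the same two windows in the final SAP and in the CGM programming specification.

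The cost is one character in the outcome table plus carrying the definition forward. Data collection, visits and sample size do not change.

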
To describe the effects of using a NFA versus a SDA during CGM initiation on additional CGM-derived metrics, components of dietary intake, other markers of health, and PROs. To describe potential behavioral mechanisms associated with change in study outcomes.

CGM Initiation in People with T2D

10. Phase 2 Study Objectives

Primary Objective

To evaluate the impact of CGM discontinuation 4 months after the completion of the Phase 1 study intervention on CGM-derived TIR.

Exploratory Objectives

To describe changes in additional CGM-derived metrics, HbA1c, dietary intake assessment, medication use, and PROs 4 months after the completion of the Phase 1 study intervention and CGM discontinuation.

11. Phase 1 Study Outcome Measures

At the end of the Phase 1 intervention, differences from baseline will be assessed within and between study arms (primary outcome). The baseline period includes an approximately 10-day assessment before the intervention begins. The intervention begins on Day 0 and stops on approximately Day 50, this includes the 10-day post-intervention assessment. The post-intervention assessment period occurs approximately Day 40 to Day 50; during this time, participants continue in their intervention arm and continue using their CGM as instructed.

CGM-related outcome measures include approximately 10 days of CGM data collection during the baseline and the post-intervention assessment periods. CGM data is collected as follows:

- Baseline: Up to 10 days of CGM data from a Dexcom G7 sensor paired with a physically blinded Dexcom receiver
- Post-intervention: Up to 10 days of CGM data from a Dexcom G7 sensor paired with apps on the participant's personal cell phone (glucose data transferred to study team via cloud)

Of note, G7 data is identical whether data is pulled through a Dexcom receiver or a participant's personal cell phone. The only difference between the two scenarios is that the participant will not be able to view their glucose data during the baseline period (blinded data).

Primary Outcome

Outcome	Assessment Method
1. Change in CGM-derived TIR (% time with glucose 70-180 mg/dL) from baseline to post-intervention	See CGM-related outcome measures described above

Secondary Outcome

Outcome	Assessment Method

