Once at least seven days of baseline G7 sensor data are confirmed, participants will receive their randomization assignment to either the NFA or the SDA arm.

Given that enrolling participants takes several months to complete, randomly permuted blocks of size two, four, and six will be used to ensure that participants are assigned to the NFA and SDA arms in approximately equal proportions over time. Randomization will be carried out within strata defined by participant's most recently available HbA1c $>8.5\%$ vs. $\leq 8.5\%$. The participant randomization schedule will be generated by the study statistician using a random number generator. Participants will remain in their assigned study arm throughout the intervention.

Blinding procedures are not described since blinding is not possible in a study comparing two different instructional approaches; the study staff and participants will know what type of instruction they give or receive. However, study participants will not know the details of the type of education provided to the other study arm (i.e. participants in the self-directed approach arm will not know the other arm is receiving a nutrition-focused approach and vice-versa).

Phase 1: Intervention

The intervention compares the effects of two different approaches used during CGM initiation, the NFA or SDA. For both arms, the intervention will include one in-person and one remote study appointment. All care and instruction will be provided by IDC research staff serving as interventionists. Intervention study staff will receive verbal training and written materials describing how to deliver the NFA and SDA; and checklists will be used to ensure consistent delivery among study staff and within each study arm.

On study Day 0, participants who have met all eligibility criteria and who have at least seven days of blinded CGM data will receive Dexcom G7 systems that will be paired with apps on their personal cell phone. Study staff will assist the participant in applying the G7 sensor, as needed. All participants will be instructed to wear and use the G7 and the associated phone apps continuously throughout the intervention, including changing out the sensors every 10 days or as needed. Intervention duration is expected to last approximately 50 days.

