
Contact 3: Remote Follow-up
 
Day 14 (+7 days)
 
Intervention
	
 • Study team saves participant’s CGM data from Clarity website immediately before remote contact • Study staff contacts participant • Diabetes medication assessment • Study staff reviews CGM data with participant and reinforces the NFA or SDA messages based on participant’s randomization arm • Participant wears the G7 sensor and uses the real-time glucose data from the associated apps until study completion • Study team documents measures of intervention fidelity

Contact 4: Post-intervention assessments begin
 
Day 40 (+7 days)
 
Intervention
	
 • Participant receives reminder from study team on approximately Day 40 to: 
 ○ Wear G7 sensor and use data from the associated apps for final 10-days of the study ○ Complete first post-intervention ASA24 diet recall

Contact 5: Post-intervention assessments ends
 
Day 50 (+7 days) (plus additional days, if needed, to obtain at least seven days of G7 sensor data)
 
Post-Intervention Assessments & Study Completion
	
 • Study team confirms at least seven days of G7 CGM data collected between approximately Day 40 and Day 50 
 ○ If a participant has fewer than seven days of CGM data, the participant will be provided an option to continue in the study until seven days of data are obtained or the participant can choose to exit the study • Study team saves participant’s CGM data from Clarity website • Participant completes post-intervention assessments, including: 
 ○ HbA1c ○ Diabetes medication assessment ○ Weight, BP ○ Complete second ASA24 diet recall and DietID assessment ○ PRO surveys (Diabetes distress, diet adherence, efficacy, intervention fidelity, post-intervention survey)

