With an expected sample size of n=54 per arm for the intention to treat (ITT) sample in Phase 2, the primary analysis has 80% power ($\alpha=.05$, two-sided) to detect an absolute change for pooled study arms of 0.27 standard deviation units of change in TIR from the end of the intervention to follow-up. For within-arm tests of change in this sample the primary analysis has 80% power ($\alpha=.05$, two-sided) to detect an absolute change within a study arm of 0.39 standard deviation units of change in TIR from the end of the intervention to follow-up.

Populations for Analysis

The analysis for Phase 1 will follow a modified intention to treat perspective, with an analysis of CGM metrics that includes only participants with at least seven days of CGM data at both baseline (approximately day -11 to -1) and post-intervention (approximately day 40 to 50).

The analysis for Phase 2 will follow a modified intention to treat perspective, with an analysis of CGM metrics that includes only participants with at least seven days of CGM data at both post-intervention and follow-up. This sample is utilized to assess the effect of discontinuation of CGM utilized in phase 1. A per-protocol (PP) analytic sample will consist of participants with at least seven days of CGM data at both post-intervention and follow-up who did not use CGM, and who did not require changes to glucose-lowering medications during the follow-up period. This PP sample is utilized to assess the effect of discontinuation on patients not utilizing CGM and having no medication adjustments during the follow-up period.

General Approach for Statistical Analyses in Phase 1

Baseline characteristics of study participants will be summarized with mean and standard deviation for interval data and proportions for categorical data. For analyses that do not concern total HEI or HEI component scores, the analytic models will utilize general and generalized linear mixed model repeated measures analysis to estimate differential change by study arm from baseline to post-intervention period. The link function and error distribution selected for each model will be based on the distribution of the endpoint. Each model will include fixed effects for study arm, time, their interaction, variables used in stratification, and a random intercept for patient. Each model will report the model-derived estimate (and 95% confidence interval) for the endpoint by study arm and by time period (baseline, day 50).

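### The two Phase 1 exploratory wear outcomes are tested after selecting on wear, in about 10 of the 50 intervention days, so they cannot describe CGM use over the intervention

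*Combined protocol and SAP*

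**What the plan says.** Section 11 (Phase 1 Study Outcome Measures), exploratory item 1, includes "number of days CGM device is worn" and the percentage of "time CGM sensor is active". Both are outcomes of change between baseline and the post-intervention period. The method is the one given for every CGM outcome: "CGM-related outcome measures include approximately 10 days of CGM data collection during the baseline and the post-intervention assessment periods". At baseline this is a blinded sensor applied by staff. At the end it is "Up to 10 days of CGM data from a Dexcom G7 sensor paired with apps" on the participant's own phone.

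Section 23, Populations for Analysis, limits the Phase 1 analysis of CGM metrics to a set that "includes only participants with at least seven days of CGM data at both baseline (approximately day -11 to -1) and post-intervention".

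Conduct follows the same threshold. Under Randomization (Section 15), no assignment is disclosed until seven baseline days are confirmed. In the Detailed Schedule of Activities, a reminder at Contact 4 (about Day 40) asks participants to wear the sensor for the last stretch. At Contact 5, a person with fewer than seven days may stay on or leave: the "participant will be provided an option to continue in the study until seven days of data are obtained". Note c to the Study Schema (Section 3) allows the window to be lengthened for this purpose.

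On the intervention itself, Section 11 states: "The intervention begins on Day 0 and stops on approximately Day 50". Section 15 tells participants in both arms to "wear and use the G7 and the associated phone apps continuously throughout the intervention". Real-time data are saved at Contacts 3 and 5.

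Section 23, Analysis of Exploratory Endpoints in Phase 1, applies the primary model to exploratory outcomes and tests the arm-by-time interaction. It also permits post-only models for some of them.

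**The concern.** A change in wear that is tested between arms will be read as saying something about how much the arms used CGM. Three features of the plan prevent that.

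- **Selection on the outcome.** Participants with low wear in the final window either continue until they reach seven days or leave the analysis set. The part of the distribution where arms would differ most is removed.
- **Baseline.** The comparator is a blinded sensor that staff apply. Wear of that sensor says little about voluntary use of real-time CGM, so subtracting it does not sharpen the measure.
- **Window.** Only the last 10 days or so count, and they open with a reminder. No listed outcome summarises sensor wear over the rest of the intervention. The fidelity outcome (Section 11, exploratory item 8) rests on staff paperwork and participant surveys and does not name sensor-recorded wear.

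What is at stake is interpretation. Section 13 attributes the expected advantage of the nutrition-focused arm to dietary improvement, and Section 9 has an exploratory objective on behavioural mechanisms. More CGM wear is another route by which that arm could gain. A small or null interaction on these two items could be taken as evidence that wear was alike, which the data as selected cannot show.

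**Working it through.** The plan gives no expected wear rate and no target figure for these items, so there is nothing to reproduce. The check uses the plan's own limits, followed by an illustration with assumed rates.

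**Inputs from the documents**
- Minimum analysed in each window: 7 days (Section 23, Populations for Analysis).
- Nominal maximum in each window: 10 days (Section 11).
- Length of the intervention: about 50 days (Section 11).

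**Share of the intervention measured**
- 10 / 50 = 20%. Left out: 50 - 10 = 40 days, or 80%.

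**Range of the outcome**
- Each window: 7 to 10 days, about 70% to 100% of a 10-day window.
- Change: from 7 - 10 = -3 to 10 - 7 = +3 days.
- These limits are approximate. The final window may be extended, and the denominator of the percentage active is then undefined.

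**What a score says about the 50 days**
- A score of 7 fits any total from 7 + 0 = 7 to 7 + 40 = 47 days.
- A score of 10 fits any total from 10 + 0 = 10 to 10 + 40 = 50 days.

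**Illustration of the seven-day rule in the final window**

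Assumptions, not taken from the documents: each day is worn independently with probability p; p is constant over the 50 days; nobody uses the option to extend. Every assigned participant has already met the baseline minimum, so only the final window selects. With X ~ Binomial(10, p):

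- share kept = P(X ≥ 7)
- mean days among those kept = E[X | X ≥ 7] = Σ x·P(X = x) / P(X ≥ 7), with x from 7 to 10

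| Assumed p | Days worn of 50 | Mean of 10, no rule | Share kept | Mean among kept |
|---|---|---|---|---|
| 0.9 | 45 | 9 | 98.7% | 9.04 |
| 0.8 | 40 | 8 | 87.9% | 8.32 |
| 0.7 | 35 | 7 | 65.0% | 7.86 |
| 0.6 | 30 | 6 | 38.2% | 7.57 |
| 0.5 | 25 | 5 | 17.2% | 7.39 |

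For p = 0.9 in one arm and 0.6 in the other:
- over the whole intervention: 45 - 30 = 15 days;
- in the final window without the rule: 9 - 6 = 3 days;
- in the final window with the rule: 9.04 - 7.57 = 1.47, about 1.5 days;
- excluded: 100 - 98.7 = 1.3% and 100 - 38.2 = 61.8%.

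The rule alone halves the visible difference in this example. For p = 0.9 against 0.8 it falls from 1 day to 9.04 - 8.32 = 0.72 day. Where participants extend instead of leaving, fewer are excluded, but their values are brought up to seven.

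**The case against.** The strongest reply is that the plan never gives these items the task of measuring adherence. They stand in a list of core CGM metrics beside mean glucose and variability, no hypothesis concerns wear, and they can be read as describing how much data lies behind each window's time in range. That stands as a reading of their purpose. It does not explain why they are set up as change outcomes with an interaction test: a data-sufficiency descriptor needs neither.

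Three stronger readings are tempting, and the documents do not support them.

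- A reader might infer that wear must look almost the same in both arms. It need not. Differences between 7 and 10 days can still show, the illustration leaves about 9.0 against 7.6 days, and unequal exclusions would themselves be visible. The difference is compressed, not abolished.
- A reader might infer that unequal wear would confound the primary result. Wear after assignment is a possible pathway of the initiation approach. The primary objective compares the two approaches on time in range, and that contrast does not depend on how wear is summarised.
- A reader might infer that CGM exposure is wholly unexamined. The survey items and intervention manuals are not part of the documents, and further exploratory detail is deferred to a final SAP. Whether CGM use is asked about elsewhere cannot be judged.

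It is also fair to say that the practical size is unknown, since no wear rate is given. Contact 3, where staff review CGM data with the participant, may keep early wear high.

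**Conclusion.** The point holds for the two exploratory wear items in Phase 1. As planned, they compare arms on wear after selecting on wear, against a baseline that is not real-time use, in about 20% of the intervention. Any arm difference is compressed, low wearers drop out of the comparison or are brought up to the threshold, and the result cannot describe CGM use over the 50 days.

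The range limits and the 80% follow directly from the plan's 7, 10 and 50 days, subject to the extendable window. The reduction from 15 to about 1.5 days rests on assumed wear of 90% and 60%, constant and independent from day to day; only its direction should be relied on.

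The consequence is confined to exploratory interpretation of mechanism, and the primary comparison is unaffected. Section 12 repeats the two items for Phase 2 as a change from self-managed real-time wear to a staff-applied blinded sensor. That contrast does not measure engagement either.

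**What to change.** In the final SAP, for Phase 1:

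1. Report days worn and percentage sensor active over Day 0 to Contact 5, and separately over Day 0 to Contact 4, before the reminder can act.
2. Present both by arm in all participants given their assignment, without the seven-day restriction, using the post-only model that Section 23 already allows.
3. Define the denominator of the percentage active, including for extended windows and for people who leave early.
4. Keep wear within the assessment windows, in Phase 1 and Phase 2, as a description of data sufficiency and not as a tested change outcome.
5. State that whole-period wear is exploratory information on mechanism, and that it records sensor wear, not how often participants look at their data.

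The source is the real-time data saved at Contacts 3 and 5. The documents do not give the date span of those downloads, so the sponsor should confirm that together they cover Day 0 to Contact 5 and that data are also saved for people who leave early. If so, the cost is revised wording in the outcome tables and SAP, a small extra computation and one more exploratory summary, with no new visit or instrument.
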